#### **4.0 THERAPEUTIC PROGRAM**

This Phase III randomized study is designed to determine if patients with locally advanced cervical cancer have longer overall survivals with pretherapeutic paraaortic surgical staging when compared to radiologic staging.

All eligible patients in MD Anderson and Lyndon B. Johnson General Hospital (LBJ) will be required to sign an informed consent prior to randomization. Patients will be equally allocated between the 2 treatment groups.

Eligible patients will be randomized to either standard chemoradiation (standard-of-care arm) or pretherapeutic paraaortic lymphadenectomy followed by tailored chemoradiation (experimental arm). Pretherapeutic lymphadenectomy will be performed via the laparoscopic extraperitoneal approach using either traditional laparoscopy or robotically-assisted laparoscopy. Patient demographic and treatment information will be collected at time of enrollment and throughout initial definitive therapy (Appendix C).

*Radiology Protocol and Definitions of Positive and Indeterminate Nodes*

All scans will be performed on a dedicated Positron Emission Tomography/Computed Tomography (PET/CT) scanner that will allow fusion of PET and CT images. Standard imaging protocols for PET/CT will be followed with non-contrast CT used for attenuation correction.

The standard definition of abnormal lymph nodes in the abdomen and pelvis by cross sectional imaging is size greater than 10 mm. Therefore nodes greater than 10 mm in the abdomen or pelvis will be considered abnormal by CT.

PET/CT images will be evaluated qualitatively for focal areas of abnormally increased 18-fluorine fluorodeoxy glucose (FDG) uptake. A positive finding is defined as the presence of abnormal FDG uptake when accumulation of the tracer is moderately to markedly increased relative to the uptake in comparable normal structures or surrounding tissues, with the exclusion of physiologic bowel and urinary activity. A negative finding is defined as no detectable FDG uptake.

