## 5.0 STATISTICAL CONSIDERATIONS

### Sample Size Estimation

Based on data collected in the recently completed phase II study at MD Anderson which enrolled 65 women (60 evaluable) with locally advanced, approximately 32% will have PET imaging showing tumor metastasis to the pelvic nodes with negative paraaortic lymph nodes. Of these women, approximately 79% will truly have negative paraaortic lymph nodes. For them, 3 year overall survival with whole pelvis radiotherapy and concurrent chemotherapy is 75%. For the approximately 21% of women with false negative imaging (i.e. pathologically positive paraaortic lymph nodes with negative imaging), the 3 year overall survival with whole pelvis radiotherapy and concurrent chemotherapy is only 10%. If these metastases were known, however, and the radiation field was extended to cover the paraaortic basins, the 3 year overall survival improves to 50%. Thus, the expected overall survival without surgical staging would be approximately 61% and with preoperative paraaortic surgical evaluation would be 70%.

Assuming an accrual rate of 10 patients per month a sample size of 600 patients will yield 80% power with a 2-sided 0.05 significance level to detect a difference in 3-year overall survival of 61% and 70% between the patients without preoperative paraaortic surgical staging and the patients with preoperative paraaortic surgical staging. Accrual would take 5 years, and the study would be expected to take 7.6 years to complete, with a maximum 348 expected deaths. The accrual at LBJ will be 15 patients.

This sample size calculation includes an interim analysis for efficacy and futility once 174 deaths have been observed. The nominal p-value for the interim analysis of efficacy is 0.0031 and the nominal p-value for the interim analysis for futility is 0.3217. The nominal p-value for the final analysis is 0.049. The spending function approach of Lan and DeMets [16] with an O'Brien-Fleming [17] boundary for the interim analysis of efficacy and a Pocock [18] boundary for the interim analysis of futility were used in the sample size estimation. East 5.0 (Copyright © 2007, Cytel Inc., Cambridge, MA) was used to estimate the sample size and plan the interim analyses.

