### Analysis

We will use descriptive statistics to summarize patient demographic and clinical characteristics by treatment group.

We will estimate overall survival (OS) with the product limit estimator of Kaplan and Meier [19], and we will estimate the 3-year OS with a 95% confidence interval. We will also estimate the median OS with a 95% confidence interval. We will use the log-rank test to compare the 2 treatment groups with respect to OS.

We will also use the log-rank test for the interim analysis of OS, which will take place after 131 deaths have been observed. If the p-value from this test is  $< 0.0031$  the study will be stopped for efficacy, and if the p-value from this test is  $> 0.3217$  the study will be stopped for futility.

We will use Cox [20] proportional hazards regression to model OS as a function of treatment and other well-known and potential prognostic factors such as clinical stage, histology, and grade. We will estimate the hazard ratio for treatment (preoperative paraaortic surgical staging vs not) and other potential prognostic factors with 95% confidence intervals.

We will perform similar analyses for disease-free survival (DFS) as for OS.

We will tabulate the numbers of patients with particular short- and long-term morbidities including intraoperative and postoperative complications and treatment delay for each treatment group, and we will use the chi-square test to compare treatment groups with respect to the incidence of these morbidities.

For the treatment arm with pretreatment paraaortic surgical staging we will estimate the sensitivity of pretreatment radiologic staging examinations to detect metastatic disease with a 95% confidence interval. The findings of the pretreatment paraaortic surgical staging will be considered the true diagnosis of metastatic disease.

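### The single interim analysis is set at 174 deaths in one place and 131 in another with the same cut-offs; following the 131 text cuts power from 80% to about 75%

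*Combined protocol and SAP*

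**What the plan says.** Section 5.0, Sample Size Estimation, describes one interim look: "This sample size calculation includes an interim analysis for efficacy and futility once 174 deaths have been observed". The maximum is given as "with a maximum 348 expected deaths", so that look is at exactly half of the planned information. The same text gives nominal p-values of 0.0031 (interim efficacy), 0.3217 (interim futility) and 0.049 (final). It names Lan-DeMets spending with an O'Brien-Fleming boundary for efficacy and a Pocock boundary for futility.

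Section 5.0, Analysis, describes the same interim test differently: "We will also use the log-rank test for the interim analysis of OS, which will take place after 131 deaths have been observed". It then says the trial will stop for efficacy if p is below 0.0031 and for futility if p is above 0.3217. The cut-offs are those of the design text; only the number of deaths differs. Neither rule says which arm the result must favour.

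**The concern.** A group-sequential cut-off belongs to an information fraction. 174 of 348 is 50%, whereas 131 of 348 is 37.6%. One pair of p-values cannot come from the same spending functions at both fractions, so at least one of the two texts does not describe the design that was powered.

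This is the trial's only numerical stopping rule for survival, and the Analysis text is what a statistician would carry out. An earlier look with an unchanged futility cut-off asks for the same strength of evidence from fewer deaths, so a trial with a real benefit is abandoned more often. The ambiguity itself also does harm: once 131 deaths have occurred, choosing between the two counts is no longer clearly independent of the data.

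**Working it through.** **Inputs, all from section 5.0, Sample Size Estimation, unless noted**
- Design: "a sample size of 600 patients will yield 80% power with a 2-sided 0.05 significance level".
- Effect: 3-year survival of 61% against 70%.
- Allocation 1:1 (section 4.0).
- Maximum 348 deaths; cut-offs 0.0031, 0.3217 and 0.049.
- Interim at 174 deaths, or at 131 (Analysis).

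**Assumptions added:** proportional hazards with exponential survival, and the final analysis at 348 deaths.

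**Effect and drift.** HR = ln 0.70 / ln 0.61 = 0.7216, so |ln HR| = 0.3263. The log-rank Z at d deaths is taken as normal with mean 0.3263 × √(d/4) and variance 1:
- d = 131: mean 1.867
- d = 174: mean 2.152
- d = 348: mean 3.044

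The correlation between the interim and final Z is √(d/348).

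**Step 1: reproduce the plan at t = 174/348 = 0.5**
- Efficacy: one-sided O'Brien-Fleming-type spend 2[1 − Φ(2.2414/√t)] = 0.001525, which is a two-sided nominal p of 0.00305 (stated 0.0031).
- Final: with futility non-binding, the final nominal p is 0.0490 (stated 0.049).
- Futility: Pocock-type beta spend 0.20 × ln[1 + (e − 1)t] = 0.124. The matching z is 2.152 + Φ⁻¹(0.124) = 0.997, p = 0.319. With the 344 deaths that give exactly 80% power it is 0.325 (stated 0.3217).
- Power with the stated cut-offs (z = 2.958, 0.991 and 1.969): stop for efficacy at the interim 21.0%, plus continue and reject at the end 59.3%, total 80.4% (stated 80%).

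The design text is therefore self-consistent at 174 of 348.

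**Step 2: the same spending functions at t = 131/348 = 0.376**
- Efficacy: nominal p = 0.0005 (z = 3.47).
- Futility: beta spend 0.100, giving p = 0.56 for a signed rule (z = 0.585) or 0.54 if p is read as strictly two-sided.
- Final nominal p = 0.0498; power with these matched cut-offs and the signed rule is 81.0%.

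The printed 0.0031 and 0.3217 do not belong to this look. As a nominal p-value, the efficacy cut-off is about six times too lenient (0.0031/0.0005).

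**Step 3: the Analysis text followed literally, final analysis at 348 deaths**

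| | Look at 174 | Look at 131 |
|---|---|---|
| Futility stop if HR = 0.7216, two-sided p | 12.2% | 18.8% |
| Futility stop if HR = 0.7216, signed rule | 12.3% | 19.0% |
| Power, futility obeyed | 80.4% | 74.6% |
| Power, futility ignored | 86.0% | 86.0% |
| Two-sided type I error, futility ignored | 5.00% | 5.05% |
| Futility stop if HR = 1, two-sided p (signed) | 68% (84%) | 68% (84%) |

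**Step 4: could 131 belong to another coherent design?** 131 is half of 262, but 262 appears nowhere and conflicts with 348. With the stated cut-offs it gives only 68.6% power.

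**Step 5: direction.** A two-sided p below 0.0031 favouring the control arm would, as worded, be an efficacy stop. An adverse trend with p between 0.0031 and 0.3217 would trigger nothing. As an illustration (the HR is my assumption), if the true HR were 1.2 against surgical staging, a look at 174 deaths would fall in that adverse gap 54% of the time. Even at the gap's most favourable edge (z = −0.99), conditional power for benefit under the design effect is only about 5%.

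**The case against.** The strongest reply is that the design text is complete and agrees with itself, so 131 is probably one stale number that any statistician would query before acting. That is likely, and it explains why the repair is small. But the Analysis text is a current instruction, and nothing in the documents marks it as superseded.

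Other points narrow the claim, and they stand:
- The cut-offs fix an information fraction, not a count. That 174 is intended is an inference from the 348 maximum, so the sponsor should confirm it against the design output.
- The power loss depends on obeying the futility rule. The stated final p of 0.049 fits a non-binding futility boundary, and if futility were ignored power would be 86.0% at either look. The Analysis text, however, makes stopping mandatory.
- The extra futility stopping arises when the benefit is real; under the null the probability is the same at both looks.
- The looser efficacy cut-off sounds worse than it is, because overall type I error barely changes.
- The direction gap is a separate and lesser point. It hardly affects power, and the independent Trial Safety Committee (section 9.1) reviews safety and efficacy data and may recommend stopping for safety reasons.

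**Conclusion.** The concern holds. The plan gives two incompatible triggers for its only formal interim analysis, and the printed cut-offs fit 174 of 348 deaths but not 131 of 348. Following the Analysis text raises the chance of abandoning a real benefit by 6.6 percentage points (18.8% − 12.2%) and lowers power by 5.8 points (80.4% − 74.6%), so the stated 80% is not delivered. The damage is to power, not to type I error. These sizes rest on proportional hazards at HR 0.7216, a final analysis at 348 deaths, and a futility rule obeyed as written. The contradiction itself rests on no assumption. It must be corrected before the interim.

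**What to change.** 1. In section 5.0, Analysis, change 131 to 174 deaths, after confirming against the sponsor's design output that 174 of 348 is the intended look.
2. If 131 is truly intended, keep the 348 maximum and replace the cut-offs with those for 37.6% information: about 0.0005 for efficacy, about 0.56 for futility under a signed rule (0.54 if strictly two-sided), and about 0.0498 at the final analysis. Restate power, and make the Sample Size Estimation text agree.
3. Write the rule on the signed log-rank statistic. For the 174-death look: efficacy only if p is below 0.0031 in favour of surgical staging; futility if z in that direction is below 0.99, which includes any trend towards harm.
4. State whether the futility boundary is binding, since the power figure depends on it.

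The cost is a short amendment, with no added patients, data or follow-up. It should be in place before the 131st death, so that the choice of trigger cannot be influenced by accumulating results.

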## **9.0 STUDY COMMITTEES**

### **9.1 Trial Safety Committee (TSC)**

An independent Trial Safety Committee (TSC) will be assembled to review the safety and efficacy data collected during the study. They will be composed of individuals who

are independent of the study and are not involved (either directly or indirectly) in the management of this study. The membership includes the following:

- 3 gynecological oncologists who are otherwise not related to the trial;
- 2 Statisticians who are otherwise not related to the trial;
- 1 public member

The TSC will be responsible for monitoring, on an ongoing basis, any of the following events:

- General Toxicity (NCI-CTC AE, v4.0): grade 3 and grade 4 adverse events, serious adverse events
- A patient death (grade 5)

The first safety analysis will be performed after 20 patients have completed treatment. All further TSC reviews should take place twice per year and the committee will review all safety data collected during the study.

Following each meeting, the committee will recommend that the study continues according to the protocol or may suggest changes to the protocol based on the outcome of the data review. In exceptional cases the committee may recommend stopping the study due to safety reasons.

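### The interim stopping rule gives no direction: read literally, it continues the trial on a moderate adverse survival trend and labels significant harm as efficacy

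*Combined protocol and SAP*

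**What the plan says.** The Sample Size Estimation part of section 5.0 plans for "80% power with a 2-sided 0.05 significance level" to detect a "difference in 3-year overall survival of 61% and 70" per cent, with a "maximum 348 expected deaths". It includes one "interim analysis for efficacy and futility once 174 deaths have been observed". The nominal p-values are 0.0031 (interim efficacy), 0.3217 (interim futility) and 0.049 (final). The efficacy boundary is O'Brien-Fleming by Lan-DeMets spending and the futility boundary is Pocock.

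The Analysis part turns this into a decision rule on the log-rank test. If p < 0.0031, "the study will be stopped for efficacy, and if the p-value from this test is" greater than 0.3217 it is stopped for futility. No favoured arm, hazard ratio sign or one-sided test is named in either limb. The same part places the look elsewhere, as one "which will take place after 131 deaths have been observed".

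Section 9.1 sets up an independent Trial Safety Committee (TSC). It reviews safety and efficacy data, monitors deaths, first reviews safety after 20 patients have completed treatment, and then meets twice a year. On stopping it says: "In exceptional cases the committee may recommend stopping the study due to safety reasons". It gives no mortality threshold and does not assign the interim rule to the committee.

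**The concern.** A two-sided log-rank p-value measures how far apart the survival curves are, not which is higher. A rule based only on its size treats a deficit with surgery exactly as it treats a benefit of the same size. A result near no difference stops the trial, a moderately worse result for surgery keeps it randomising, and a clearly worse result meets the efficacy criterion.

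The experimental arm adds an operation and, for some women, a larger radiation field. The primary objective is longer survival with surgical staging. Excess death in that arm is therefore what the interim look should be able to recognise, and this is the only numerical stopping rule in the plan.

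**Working it through.** **Inputs.** Section 5.0: 3-year survival 61% and 70%, two-sided 0.05, 80% power, 348 deaths, interim at 174 (or 131), cut-offs 0.0031, 0.3217 and 0.049, 10 patients a month, 600 in total. Section 4.0: "Patients will be equally allocated between the 2 treatment groups".

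**1. Reproducing the plan's figures.** Under proportional hazards the design hazard ratio (HR) is ln(0.70)/ln(0.61) = 0.722. I used Lan-DeMets O'Brien-Fleming alpha spending, Pocock-type beta spending and an information fraction of 174/348 = 0.50.

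| Futility boundary | Interim efficacy p | Interim futility p | Final p |
|---|---|---|---|
| Stated in plan | 0.0031 | 0.3217 | 0.049 |
| Two-sided symmetric, non-binding | 0.00305 | 0.32167 | 0.0490 |
| One-sided, non-binding | 0.00305 | 0.3249 | 0.0490 |
| Binding (either) | 0.00305 | 0.352 to 0.356 | about 0.060 |

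Only the two-sided symmetric, non-binding version matches all three. It needs about 345 deaths (348 stated), and power at 348 is 80.2%. The plan does not state the sidedness of its interim p-values, but they behave as two-sided.

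**2. Cut-offs on the Z scale.** Two-sided p = 0.0031 gives |Z| = 2.958, and p = 0.3217 gives |Z| = 0.991.

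**3. Zones by observed HR (surgery versus standard).** With 1:1 allocation the standard error of ln(HR) is about 2/√D, so the cut points are exp(±0.991 × 2/√D) and exp(±2.958 × 2/√D).

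| Literal decision | 174 deaths | 131 deaths |
|---|---|---|
| Efficacy, surgery better | below 0.639 | below 0.596 |
| Continue, surgery better | 0.639 to 0.860 | 0.596 to 0.841 |
| Futility | 0.860 to 1.162 | 0.841 to 1.189 |
| Continue, surgery worse | 1.162 to 1.566 | 1.189 to 1.677 |
| Efficacy by label, surgery worse | above 1.566 | above 1.677 |

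For example, at 174 deaths an observed HR of 1.10 has Z = ln(1.10) × √174/2 = 0.63 against surgery, p = 0.53, and stops. An HR of 1.30 has Z = 1.73, p = 0.08, and continues. An HR of 1.60 has Z = 3.10, p = 0.002, and is called efficacy.

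**4. Probabilities at 174 deaths.** Z in favour of surgery is approximately N(−ln(HR) × √174/2, 1).

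| True HR | Futility stop | Continue, adverse trend | Harm labelled efficacy | Futility stop under a signed rule |
|---|---|---|---|---|
| 1.0 | 67.8% | 15.9% | 0.16% | 83.9% |
| 1.2 | 40.2% | 54.4% | 4.0% | 98.6% |
| 1.3 | 22.7% | 66.0% | 11.0% | 99.7% |
| 1.5 | 4.6% | 56.5% | 38.8% | >99.9% |
| 1.6 | 1.8% | 42.6% | 55.7% | >99.9% |

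Continuation on an adverse trend peaks at about 67%, near a true HR of 1.35, and then falls. At 131 deaths, for true HR 1.2 / 1.3 / 1.5, it is 49% / 62% / 65%, and the mislabelled stop is 3% / 7% / 26%.

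**5. Women affected.** Assume exponential survival with standard-arm hazard λ = −ln(0.61)/3 = 0.165 a year, surgery hazard h × λ (h being the true HR), and 60 women a year per arm. Solve 60[t − (1 − e^(−λt))/λ] + 60[t − (1 − e^(−hλt))/(hλ)] = 174 for t. For h = 1.2 / 1.3 / 1.5, t is 4.55 / 4.47 / 4.33 years, with about 546 / 536 / 519 women enrolled. Half of the remainder gives about 27 / 32 / 41 still to be assigned to surgery if the trial continues. Multiplied by the chance of continuing on an adverse trend, this is about 15 / 21 / 23. For a look at 131 deaths, the numbers left to assign are about 67 / 72 / 79.

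**6. Cost of a signed rule.** At the design HR of 0.722, the chance of a futility stop moves from 12.2% to 12.3%. Power for benefit falls by about 0.003 percentage points.

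**The case against.** The strongest reply has three parts.

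- **Two-sided symmetric boundaries are a legitimate design.** The plan specifies a two-sided test, and continuing under an adverse trend preserves the chance of showing that surgery is worse. This stands as a possible choice, but the plan does not say it is being made, and calling both tails efficacy argues against it. Reading direction into the efficacy limb alone is not enough. Observed HRs of 1.16 to 1.57 would still continue, because their p-values lie below 0.3217.
- **The TSC protects patients.** It is independent, includes two statisticians, reviews efficacy as well as safety data, monitors every death and meets twice a year. A reader might infer from the rule that nothing could stop a harmful trial, and section 9.1 does not support that. The safeguard is discretionary, however, and stands beside a written rule that says continue.
- **The mislabelled tail is a fault of conclusion.** When p < 0.0031 against surgery, enrolment stops, and the planned Kaplan-Meier estimates and hazard ratio would show the direction. This stands. The 4%, 11% and 39% are trials that stop.

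Two other stronger readings fail. One is that the worse surgery does, the likelier the trial is to continue; this holds only up to a true HR of about 1.35. The other is that a neutral trial is sure to stop; at a true HR of 1.0 the chance of a futility stop is about 68%.

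**Conclusion.** The concern holds as a defect in the written rule. Followed literally at 174 deaths, the rule continues when the observed HR is between 1.16 and 1.57 against surgery, and reports efficacy above 1.57. For true HRs of 1.2 to 1.5, continuing on an adverse trend is more likely than not (54% to 66%). The direction fault is the same at 131 deaths.

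This rests on reading the cut-offs as two-sided, which the reproduction supports, and on the usual normal approximation to the log-rank statistic. The counts of women also assume exponential survival and the planned accrual of 10 a month. The figures 27 / 32 / 41 apply only if the trial continues and should not be read as the expected number. The HRs above 1 are illustrations; the documents report no excess mortality with surgery. It should be fixed before the interim look, because the rule gives a wrong instruction when followed and is easily corrected.

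**What to change.** Restate the rule in the Analysis part of section 5.0 on the signed log-rank statistic, keeping the cut-offs:

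- **Efficacy:** two-sided p < 0.0031 with the hazard ratio favouring surgical staging.
- **Futility:** Z in favour of surgical staging below 0.991 (HR above about 0.86 at 174 deaths). This includes every result favouring the standard arm.
- **Harm:** p < 0.0031 against surgical staging is reported as harm, not efficacy.

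Add a sentence to section 9.1 that the TSC applies this rule.

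The cost is about three sentences. Cut-offs and sample size are unchanged, and the loss of power is negligible. The small downside is that the trial would no longer continue merely to show that surgery is significantly worse. If the sponsor wants to keep that option, the protocol should say so and justify it.

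The conflict between 174 and 131 deaths is a separate point that must also be reconciled. The HR equivalent of Z = 0.991 depends on it (about 0.84 at 131 deaths).

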### **1.2 Secondary Objectives**

- 1.2.1 To determine if patients with locally advanced cervical cancer have longer disease-free survival with pretherapeutic paraaortic surgical staging when compared to radiologic staging.
- 1.2.2 To determine short- and long-term morbidity of pretherapeutic surgical staging in patients with locally advanced cervical cancer
- 1.2.3 To determine sensitivity of pretreatment staging radiologic examinations in detecting metastatic disease.
- 1.2.4 To determine site of paraaortic metastatic disease along aorta as related to the inferior mesenteric artery (i.e. above or below) in patients with locally advanced cervical cancer
- 1.2.5 To evaluate surgical complication rates of the laparoscopic extraperitoneal paraaortic lymphadenectomy in a large cohort of patients.

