## **7.2 Common Adverse Events**

The most common postoperative adverse events from study treatment include:

- Intraoperative injury (bowel, bladder, ureter, nerves or blood vessels)
- Wound complication (vault or pelvic hematoma or collection)
- Infectious complications (bladder, chest, septicemia)
- Postoperative hemorrhage/ bleeding, thromboembolic events (DVT, pulmonary embolus)
- Prolonged Ileus > 7 days, fistula formation (any) or hernia formation
- Cardiac, pulmonary renal or cerebrovascular complications
- Returned to theatre in same admission (re-operation)
- Bladder dysfunction
- Lymphoedema

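### Complications that only the staging operation can cause are tested between arms against a zero fixed by design, while the procedure's own complication rate has no planned interval or operated-patient denominator

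*Combined protocol and SAP*

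**What the plan says.** The Analysis part of section 5.0 covers morbidity in one sentence. It tabulates "short- and long-term morbidities including intraoperative and postoperative complications and treatment delay for each treatment group" and adds that "we will use the chi-square test to compare treatment groups with respect to the incidence of these morbidities". No event type is exempted, and neither a continuity correction nor a denominator is stated.

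Section 4.0 gives the standard arm chemoradiation without lymphadenectomy; only the experimental arm has the staging operation. On allocation it says: "Patients will be equally allocated between the 2 treatment groups".

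Two secondary objectives depend on that one sentence. Objective 1.2.2 concerns the short- and long-term morbidity of surgical staging. Objective 1.2.5 reads: "To evaluate surgical complication rates of the laparoscopic extraperitoneal paraaortic lymphadenectomy in a large cohort of patients". Section 5.0 plans 95% intervals for 3-year and median survival, for hazard ratios, and for imaging sensitivity in the staged arm. It plans none for the rate in objective 1.2.5.

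**The concern.** A between-arm test is informative when both arms could have the event. Intraoperative injury needs an operation. In an arm without one, the count is zero before any patient is enrolled, apart from women staged outside the protocol. Equal incidence is then known to be false from the start, and rejecting it tells the reader only that one arm had surgery.

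Objective 1.2.5 is a one-arm question: how often does this procedure cause complications, and how precisely is that known? The plan answers with a count per treatment group. Section 4.0 shows why the randomised arm is not the right denominator. The extraperitoneal dissection goes ahead only if laparoscopy shows no intraperitoneal disease. The surgeon may also convert to a transperitoneal or open approach, or stop. Without a stated rule, different analysts could divide the same count by different numbers.

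At stake is a safety table with significant p-values for operation-specific events that carry no information, and with no stated precision for the rate that surgeons and patients need.

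**Working it through.** **Inputs.** The Sample Size Estimation part of section 5.0 states that "a sample size of 600 patients will yield 80% power with a 2-sided 0.05 significance level". With equal allocation (section 4.0), that is 600 / 2 = 300 per arm. The documents give no complication rate, target precision or sample size for morbidity, so there is no figure of the plan's own to reproduce here. Event counts and rates below are assumptions shown as a range, with all 300 experimental patients operated on.

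**Step 1: which events are fixed at zero.** Intraoperative injury, in the section 7.2 list, cannot occur without the operation. Return to theatre also presupposes one. Other listed events can occur in either arm: infection, thromboembolism, fistula, bladder dysfunction, lymphoedema, and cardiac, pulmonary, renal or cerebrovascular complications. Treatment delay can also occur in either arm.

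**Step 2: what the test does against a fixed zero.** For x/300 versus 0/300 the uncorrected statistic is N(ad − bc)² divided by the product of the four margins. With x = 4 this is 600 × (4 × 300)² / (300 × 300 × 4 × 596) = 4.03, so p = 0.045.

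| Events (experimental vs standard) | Uncorrected p | Continuity-corrected p | Fisher p |
|---|---|---|---|
| 3 vs 0 | 0.082 | 0.247 | 0.249 |
| 4 vs 0 | 0.045 | 0.132 | 0.124 |
| 5 vs 0 | 0.025 | 0.072 | 0.061 |
| 6 vs 0 | 0.014 | 0.040 | 0.030 |

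Significance needs 4 events uncorrected, or 6 with either alternative. If X is binomial(300, p), the chance of at least 4 events is 35% at a true rate of 1%, 85% at 2%, 98% at 3% and over 99.9% at 5%. The chance of at least 6 is 8%, 56%, 89% and 99.8%. For operation-specific events the result thus depends only on how common they are in operated women, a question that a rate answers directly.

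**Step 3: what can be estimated.** The exact (Clopper-Pearson) limits are the 0.025 quantile of Beta(x, 300 − x + 1) and the 0.975 quantile of Beta(x + 1, 300 − x).

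| Events / operated | Rate | Exact 95% CI |
|---|---|---|
| 0/300 | 0% | upper limit 1.2% |
| 4/300 | 1.3% | 0.4% to 3.4% |
| 9/300 | 3.0% | 1.4% to 5.6% |
| 15/300 | 5.0% | 2.8% to 8.1% |

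Fewer operated women would widen these intervals slightly.

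**Step 4: is the chi-square test itself at fault for shared events?** The exact unconditional size of the uncorrected test was computed at nominal 0.05, with 300 per arm and a common event rate. It is 0.004 at 0.2%, 0.030 at 0.5%, 0.046 at 1% and 0.049 at 2%, and never above 0.0515 for rates from 0.2% to 8%. The test holds its level.

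**Step 5: are shared events counted alike?** Section 7.1 defines treatment-emergent events relative to surgery, asks for reporting of listed events after surgery, and leaves out events related to chemoradiation. Section 7.5 collects from consent to 6 months after treatment. The standard arm has no surgery date, so only the section 7.5 rule can apply to it.

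**The case against.** The strongest reply is that most of the morbidity sentence is sound. It covers long-term morbidity, treatment delay and many events that either arm can have. For those a randomised comparison is legitimate and is what objective 1.2.2 needs. This stands: a reader might infer that the whole planned test is meaningless, and the documents do not support that.

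A reader might also infer from the gap between 0.045 and 0.124 at 4 versus 0 that chi-square is anti-conservative with sparse data. Step 4 shows otherwise. Nor is a type I error possible where the null is false by design, so the gap shows no harm there. The plan also leaves room for a continuity correction, under which 4 versus 0 is not significant.

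Third, the counts will be tabulated by group, so a reader given a denominator could work out an interval. That also stands: the rate is not lost, but its interval and its denominator are unplanned. How many women will not be operated on cannot be told from the documents.

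Finally, this is a secondary safety table. The sample size and stopping rules do not use its p-values, and the safety committee in section 9.1 reviews events separately. That limits the weight of the point. It does not make the test informative for operation-specific events.

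**Conclusion.** The point holds for operation-specific complications. There the planned p-value compares the staged arm with a zero set by design, and the one-arm rate that objective 1.2.5 asks for has neither an interval nor an operated-patient denominator. The plan already uses the right form for its other one-arm quantity, imaging sensitivity.

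It does not extend to events and delays possible in both arms. That comparison is valid in principle and should stay, provided both arms are ascertained alike, which sections 7.1 and 7.5 do not yet secure.

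The size of the issue is modest. Over the assumed range of 4 to 15 events in 300 operated women, the missing information is an interval about 3 to 5 percentage points wide (3.4 − 0.4 = 3.0; 8.1 − 2.8 = 5.3). This rests on 300 women per arm, all 300 experimental patients operated on, and no staging surgery in the standard arm. It is a cheap improvement, and the primary survival analysis is unaffected.

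**What to change.** In section 5.0, split the morbidity sentence in two and name in advance which events fall in each part.

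- **Operation-specific events:** number, percentage and exact 95% CI among women in whom the laparoscopic extraperitoneal procedure was started. Keep conversions and discontinuations in the denominator and count them. Make no between-arm test. Define what counts as started, so that women whose operation ended at the diagnostic laparoscopy are handled by rule and reported.
- **Events and delays possible in both arms:** keep the comparison by randomised arm, add a risk difference with 95% CI, and count from a common origin such as randomisation. Say whether the chi-square test is continuity-corrected. Fisher's test is optional.

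In section 7, reconcile the surgery-based definition and reporting rule in 7.1 with the collection from consent in 7.5, so that the same events are recorded over the same period in both arms. State how the exclusion of chemoradiation-related events applies to listed events that either treatment could cause.

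The cost is a small wording change in sections 5 and 7 and the loss of an uninformative p-value. If case report forms already follow the surgery-based definition, they would need checking too.
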